#### 3.1.3 Primary Outcome Measures and Justification

Patients switched to the belatacept-based regimen will be compared to a group of matched patients on standard CNI-based immunosuppression regimen on the following primary outcome measures: (1) the donor specific antibody level, (2) the frequency of alloantigen and viral antigen reactive cells as measured by cell surface cytokine analysis, and (3) the frequency of immunophenotypes described below at Month 6. Matching will be performed based on age within 10 years, sex, deceased versus living transplant, and DSA level at time of enrollment.

The intent is to investigate differences in these measures as a means to determine the immunologic mechanism of action of belatacept. These endpoints were selected based on previous research showing that these measures are key determinants of immune function in transplant patients. In addition, baseline levels at time of enrollment of these endpoints will be compared with results from months 1, 3, and 6, as well as month 12 if patients elect to continue for an additional 6 months of belatacept therapy. Month 6 will be used as the primary measure of outcome for the immunologic assays, with months 1, 3 and 12 if applicable as the secondary measures.

To perform these mechanistic studies, blood from subjects will be collected at each study time point as described below and peripheral blood mononuclear cells (PBMCs) will be isolated and frozen for future analysis.

For analysis of response to alloantigen stimulation, PBMCs will be incubated with either intact donor cells or membrane preparations from donor cells to test either direct or indirect immunity, respectively. Following incubation, a cocktail of fluorescent-conjugated monoclonal antibodies will be added to detect relevant immunologic subclasses of cells as well as relevant surface cytokines and the percentage of each lymphocyte subset will be analyzed using flow cytometry according to previously published protocols developed at the UCLA Immunogenetics Center [7].

For analysis of response to viral antigens, PBMCs will be extracted and stored as described above using well-characterized CMV or EBV antigens for stimulation during the incubation period using a similar protocol adapted for detection of relevant antiviral immune lymphocytes.

Overall immune profile will also be analyzed by immunophenotyping using multiparameter flow cytometry using the panels described below:

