#### 4 STATISTICAL METHODOLOGY 4.1 Data Set Descriptions

Data sets will be generated for all patients enrolled in the study with recorded frequency of alloantigen specific cells at weeks 0, 4, 12, and 24 after study start after both direct and indirect stimulus, frequency of anti CMV and anti EBV specific cells at weeks 0, 4, 12, and 24, and frequency of cell populations as determined by immunophenotyping analysis at weeks 0, 4, 12, and 24. A representative group of 20 control patients receiving standard immunosuppressive medications will be identified from an ongoing observational study at our center using matching criteria described above. Patient matching will be performed in a blinded fashion. The ongoing observational study at UCLA is led by [name] and all patients undergoing kidney transplantation at UCLA are eligible for enrollment for an ongoing evaluation of immunologic predictors of rejection. PBMCs have been aliquoted and stored from these patients at time points post transplantation similar to those described in this protocol so they will be an ideal source for comparative analysis.

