#### 4.2 Analyses

#### Immunologic mechanisms

Primary endpoints will be patient immune analysis at 24 weeks (end of study) as compared with control patients at a comparable time point for DSA, frequency of alloantigen and viral antigen reactive cells, and frequency of the immunophenotypes described above, comparison to be performed by Mann Whitney U test. In addition, a comparison will be made between patients' baseline and week 24 levels. ANOVA repeated measurement analysis will be used to evaluate immune measurements taken over time as compared with control patients

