#### Efficacy and safety

As an additional primary analysis, subject and graft survival at 6 months will be determined within each group. GFR measured at baseline and months 1, 3, 6, and 12 months will be descriptively summarized. Cumulative rates of acute and chronic rejection, and chronic allograft nephropathy, will be summarized, as well as incidence of post-transplant diabetes.

All AEs and SAEs since transplantation will be summarized for the patients receiving belatacept. For the control patients, rates of rejection, PTLD, and death will be summarized.

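### Banked controls have no index date and no rule for a missing week-24 sample, so selection may favor survivors; the net direction of bias is uncertain

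*Combined protocol and SAP*

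**What the plan says.** On the source of controls, Section 4.1 states: "A representative group of 20 control patients receiving standard immunosuppressive medications will be identified from an ongoing observational study at our center". It supports the choice by noting that "PBMCs have been aliquoted and stored from these patients at time points post transplantation similar to those described in this protocol".

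On matching, Section 3.1.3 states: "Matching will be performed based on age within 10 years, sex, deceased versus living transplant, and DSA level at time of enrollment". Section 4.1 adds: "Patient matching will be performed in a blinded fashion". It does not say what the matching is blinded to.

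On the immune endpoints, Section 4.2 compares week-24 values "as compared with control patients at a comparable time point", and also plans a repeated-measures ANOVA against controls.

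On clinical outcomes, Section 4.2 makes survival a further primary analysis: "subject and graft survival at 6 months will be determined within each group". It then says: "For the control patients, rates of rejection, PTLD, and death will be summarized".

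Sections 2.1 and 3.1.3 describe the survival comparison differently. Both use conventionally treated patients at the center and count from transplant. Section 2.1 looks at 12 months, and Section 3.1.3 at 6 and 12 months.

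**The concern.** Belatacept subjects are enrolled at consent, before any outcome is known, and Section 6.6 asks that all of them be followed. Controls are identified from an existing bank. The plan wants 20 of them, and each must supply a late value for the primary immune comparison. Nothing says what to do with a candidate who matches but has no late sample. Passing over that patient is the natural way to reach 20 usable controls, and it conditions selection on something that happens after follow-up starts.

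A patient who died before the late time point cannot have that sample. If the 20 chosen in this way also supply control survival, their early deaths drop out of the comparison. The hypothesis in Section 1.1 claims safety and rejection rates comparable with controls, so with 20 per group one or two missing events can change how the result reads. The control immune values would likewise come only from patients who remained in follow-up.

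**Working it through.** **Inputs.** There are 20 subjects and 20 controls (Sections 3.1.2 and 4.1). Entry is 0 to 3 months after transplant (Section 7.2.1), so week 24 falls roughly 6 to 9 months after transplant. Section 3.4 gives no alpha, power or event rate behind the 20, so there is no figure to reproduce. Section 7.3.6 gives only a first-year acute rejection rate of about 10%, with no rate for death or graft loss. I therefore assume a risk r of 2%, 5% or 10%, equal in both groups.

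**1. What selection uses.** The written matching factors are age, sex, donor type and DSA at enrollment. Time since transplant, an index date, and being alive with a functioning graft on that date are absent. For a subject, enrollment is the day of consent; for a control, it is not defined.

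**2. Six months from the switch.** Expected events in 20 unselected patients are 20r. The chance of at least one is 1 − (1 − r)^20.

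- r = 2%: 0.4 events; 1 − 0.98^20 = 33%
- r = 5%: 1.0 event; 1 − 0.95^20 = 64%
- r = 10%: 2.0 events; 1 − 0.90^20 = 88%

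If every control had to have the late sample, and no event could precede it, controls would show none of these. The bias in the risk difference would then equal r. This is an upper bound.

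**3. Twelve months from transplant.** With a constant hazard and 12-month risk p, a control required to have a sample at month L has remaining risk 1 − (1 − p)^((12 − L)/12). For p = 5%:

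- L = 6: 1 − 0.95^0.5 = 2.53%, so 1 − 2.53/5 = 49% of control events are missed
- L = 9: 1 − 0.95^0.25 = 1.27%, so 75% are missed

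Over p = 2% to 10%, the share missed is 49% to 50% at month 6 and 74% to 75% at month 9.

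**4. The opposing effect.** A subject switched at month 3 must have survived until then. With p = 5%, the risk by 6 months after transplant is 1 − 0.95^(3/12) = 1.27% for such a subject. For a control counted from transplant it is 1 − 0.95^(6/12) = 2.53%. In 20 patients that is 0.25 against 0.51 expected events, which favors belatacept. Section 5.2 also excludes subjects with biopsy-proven rejection in the first three months. No such condition is stated for controls, so the rejection comparison tilts the same way.

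**5. Effect on a formal test.** Against 0/20 controls, a two-sided Fisher exact test needs 5/20 belatacept events to reach p < 0.05 (p = 0.047; 4/20 gives p = 0.106).

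**The case against.** A reader might infer that control survival is close to 100% by construction and that belatacept must therefore look worse. The documents do not support that, for four reasons.

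- No section makes a week-24 sample, or survival to week 24, a criterion for controls. The sentence on stored samples describes the cohort. The blinding of the matching might cover later outcomes, although the plan does not say so.
- It is not settled that the 20 matched controls supply control survival. That is the natural reading of Section 4.2, but Sections 2.1 and 3.1.3 point to conventionally treated patients at the center. Sample availability need not affect that comparator.
- Section 4.2 expects to count control deaths, and a patient who loses a graft can still give blood. Zero control events is therefore an extreme case.
- Survival to the switch and the rejection exclusion work in belatacept's favor when time runs from transplant.

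It is also fair that belatacept follow-up is not unconditional. Section 6.6 provides for withdrawal that can end vital-status follow-up, and week-24 belatacept values also come only from patients who could be sampled. A between-group bias in the immune results is therefore not shown. Finally, Section 3.4 calls the work exploratory, no survival test is specified, and step 5 shows that 0.4 to 2 missed events would rarely change a p-value.

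All of this limits certainty, size and direction, but the gap remains. A missing belatacept sample is visible as one of 20, whereas a control passed over for lack of a sample leaves no trace.

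**Conclusion.** The concern holds in conditional form. The plan does not define control time zero, does not match on time since transplant, gives no rule for a control without the late sample, and names the survival comparator and time point inconsistently. If sample availability drives selection, up to 0.4 to 2 control events of 20 would be missed over 6 months, at an assumed 2% to 10% risk of death or graft loss. Only deaths are certain to be missed in that case. Survival would then be biased against belatacept, and control immune values would be limited to patients still in follow-up. If survival runs from transplant, the entry conditions for belatacept subjects pull the other way, so the net direction cannot be stated. The event rates are assumptions. The point matters for how a small descriptive comparison reads, more than for any formal test.

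**What to change.** In Section 4.1, select each control at an index date set at the same time since transplant as the matched subject's Day 1. Candidates should be observational-study patients who, on that date, are alive with a functioning graft, meet the same rejection-free condition that Section 5.2 sets for subjects, and have an index sample. Use only information known on that date, and state that those doing the matching cannot see later samples or outcomes.

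Lock the list and do not replace a control whose later sample is missing. Handle that value as missing data under one rule for both groups; the plan currently states none for either. Count death, graft loss and rejection in all 20 controls from the index date, whether or not a later sample exists.

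Reconcile Sections 2.1, 3.1.3 and 4.2 so that survival has one comparator, one starting point and stated time points.

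The cost is protocol and SAP wording and a different query of the bank. The downside is that some controls may lack a week-24 sample, which slightly reduces the immune comparison.

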#### 4.2 Analyses

#### Immunologic mechanisms

Primary endpoints will be patient immune analysis at 24 weeks (end of study) as compared with control patients at a comparable time point for DSA, frequency of alloantigen and viral antigen reactive cells, and frequency of the immunophenotypes described above, comparison to be performed by Mann Whitney U test. In addition, a comparison will be made between patients' baseline and week 24 levels. ANOVA repeated measurement analysis will be used to evaluate immune measurements taken over time as compared with control patients

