Statistical Methods: A sample size of 20 subjects will be enrolled. Because of the exploratory nature of this study is not possible to estimate power for this study size. Comparison between groups will be performed by Mann Whitney U test. In addition, a comparison will be made between patients' baseline and week 24 levels. ANOVA repeated measurement analysis will be used to evaluate immune measurements taken over time as compared with control patients.

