10.5 Institutional Review Board (IRB)
10.6 Records Retention
11 GLOSSARY OF TERMS AND LIST OF ABBREVIATIONS
11.1 Glossary of Terms
11.2 List of Abbreviations
12 REFERENCES

#### **1 INTRODUCTION**

1.1 Research Hypothesis

**Primary Hypothesis:** 

Conversion from CNI-based therapy to belatacept will be safe and effective for prevention of rejection, with a significant impact on antibody and T cell-mediated immune response as compared with control patients as measured in peripheral blood at 6 months after belatacept conversion.

Outcomes to be tested:

- Belatacept-treated subjects will not have a greater incidence of SAEs as compared with control patients
- Belatacept-treated subjects will have similar rates of acute rejection as compared with control patients
- Belatacept-treated subjects will have a lower donor-specific antibody level at 6 months compared with control patients
- Belatacept-treated subjects will have a decrease in the frequency of alloantigen specific T cells over time as compared with control patients
- Belatacept-treated subjects will have a decrease in the frequency virus specific T cells over time as compared with control patients
- Belatacept-treated subjects will have a greater percentage of naïve and central memory T cells and a lower percentage of activated T cells as compared with control patients

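### The primary week-24 Mann-Whitney test ignores the week-0 value of the same immune marker, in a non-randomised comparison that is not matched on it

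*Combined protocol and SAP*

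**What the plan says.** The Synopsis (Statistical Methods) states: "Comparison between groups will be performed by Mann Whitney U test". Section 4.2 applies that test at 24 weeks to DSA, to alloantigen- and virus-reactive cell frequencies, and to the "frequency of the immunophenotypes described above, comparison to be performed by Mann Whitney U test". Section 3.1.3 confirms Month 6 as the primary time point.

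Controls come from a separate observational cohort. On comparability, section 3.1.3 says: "Matching will be performed based on age within 10 years, sex, deceased versus living transplant, and DSA level at time of enrollment".

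Week-0 values are planned. Section 4.1 begins "Data sets will be generated for all patients enrolled in the study with recorded frequency of alloantigen specific cells" and lists weeks 0, 4, 12 and 24 for the T-cell and phenotype markers. For controls it offers stored PBMCs from similar post-transplant times; no control week 0 is defined.

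Two other analyses use baseline:
- Section 3.1.3 says "baseline levels at time of enrollment of these endpoints will be compared with results from months 1, 3, and 6", and section 4.2 repeats this for week 24. As written, this is a within-patient comparison with no named test.
- Section 4.2 adds: "ANOVA repeated measurement analysis will be used to evaluate immune measurements taken over time as compared with control patients". It gives no model term or contrast and does not call this analysis primary.

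Two hypotheses in section 1.1 concern change relative to controls: "Belatacept-treated subjects will have a decrease in the frequency of alloantigen specific T cells over time as compared with control patients" and "Belatacept-treated subjects will have a decrease in the frequency virus specific T cells over time as compared with control patients".

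**The concern.** In a non-randomised comparison, a week-24 difference mixes any drug effect with whatever difference existed before the switch. A week-0 difference is plausible here, though not shown. Subjects are selected for CNI toxicity (section 3.2). Section 5.2 also excludes early biopsy-proven rejection, PRA of 30% or more, zero HLA mismatch, and EBV-negative recipients of EBV-positive grafts. No section applies these criteria to controls. Rejection history and EBV status bear directly on alloreactive and EBV-specific T cells, which are primary endpoints. Induction agent may also differ and is not matched.

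DSA is a separate case. It is measured at baseline (sections 7.1 and 7.3.4) and already matched, so adjustment there would gain efficiency only.

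The study's aim is mechanism. Reading a pre-existing difference as a belatacept effect would be a wrong conclusion on exactly that point. A week-24-only test also does not address the two hypotheses about a decrease over time.

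**Working it through.** **Plan's own figure.** There is none to reproduce: section 3.4 says power cannot be estimated.

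**Inputs from the documents.** 20 subjects and 20 controls; markers at weeks 0, 4, 12 and 24; primary comparison at week 24.

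**Assumptions.** Two-sided 5%; unit-SD normal values; equal correlation r between visits, r = 0 / 0.3 / 0.5 / 0.7; a week-0 gap of 0.5 SD (0.25 and 0.8 SD also run); a drug effect of 0, or a 0.8 SD decrease. A *regressing* gap is 0.5 SD at week 0 and 0.5r later. A *stable* gap is 0.5 SD throughout.

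**Hand check.** For a standardised difference d, the Mann-Whitney shift is d × √(20/2) × √0.955 = 3.09d, and the rejection rate is about Φ(3.09d − 1.96) + Φ(−3.09d − 1.96).

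- Week-24 test, regressing gap: d = 0.5r. At r = 0.7, d = 0.35, shift 1.08, about 19%.
- Week-24 test, stable gap: d = 0.5, shift 1.55, about 34%.
- ANCOVA: d = (week-24 gap − r × week-0 gap)/√(1 − r²). Regressing: numerator 0.5r − 0.5r = 0, so 5%. Stable: d = 0.5√((1 − r)/(1 + r)). At r = 0.5, d = 0.289, shift 0.89, about 14%.
- Change from week 0: d = (week-24 gap − week-0 gap)/√(2(1 − r)). Regressing, r = 0.5: d = −0.25, about 12%. Stable: d = 0, so 5%.
- ANOVA group main effect, stable gap: the four-visit mean has variance (1 + 3r)/4. At r = 0.5, d = 0.5/0.791 = 0.632; t-test shift 0.632 × √10 = 2.0, about 52%.

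**Simulation (20,000 replicates per cell).** These are the figures relied on; the hand values agree to within about 2 points. With no gap and no effect, every method rejected 4.8–5.2%.

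False positives (%), no drug effect, 0.5 SD week-0 gap, r = 0 / 0.3 / 0.5 / 0.7:

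| Analysis | Regressing gap | Stable gap |
|---|---|---|
| Week-24 Mann-Whitney (planned primary) | 5 / 7 / 11 / 18 | 32 / 32 / 32 / 33 |
| Rank ANCOVA on week 0 | 5 / 5 / 5 / 5.5 | 30 / 20 / 14 / 10 |
| Mann-Whitney on change | 18 / 14 / 12 / 9 | 5 throughout |
| ANOVA group-by-time | 17.5 / 13 / 11 / 9 | 5 throughout |
| ANOVA group main effect | – | 87 / 61 / 50 / 42 |

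With a 0.25 SD gap the planned test rejects 5–8% (regressing) or 11–12% (stable). Requiring both rank ANCOVA and change to be significant gave at most 2.6% in every cell run.

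Power (%), 0.8 SD decrease, same r:

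| Analysis | No gap | Opposing stable 0.5 SD gap |
|---|---|---|
| Week-24 Mann-Whitney | 67 | 14–15 |
| Rank ANCOVA | 67 / 70 / 77 / 89 | 14 / 26 / 42 / 69 |
| ANOVA group-by-time (full effect from week 4) | 42 / 56 / 73 / 92.5 | 41 / 56.5 / 73 / 93 |
| Both ANCOVA and change | 36 / 48 / 62 / 83 | – |

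**Robustness.** With 30% or 50% of values tied at a floor, type I error of the Mann-Whitney and rank ANCOVA was 4.5–5.1%. At a 30% floor, power was 60% against 60 / 63 / 69 / 81%. If correlation decays with time (r = 0.3 / 0.5 / 0.7 between weeks 0 and 24), uncorrected group-by-time rejects 6.1 / 6.2 / 7.0%; with Greenhouse-Geisser it rejects 4.7 / 4.6 / 4.9%.

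**The case against.** The strongest objection is that rank ANCOVA is not clearly the best choice. Under a stable gap the ANOVA already planned, read as group-by-time, holds 5%, while rank ANCOVA rejects 10–30%. At a stable 0.8 SD gap rank ANCOVA rejects 60 / 39 / 28 / 18% (Mann-Whitney 67%). Nothing in the documents says whether a gap would regress or persist. This stands: no single analysis is safe in both cases. But group-by-time rejects 9–17.5% under a regressing gap. Its power also depends on timing: with linear onset to week 24 it is about 33 / 45 / 61 / 84%, and section 6.2.1 completes the CNI taper only on day 29. Rank ANCOVA, by contrast, was no worse than the planned test in any null, no-gap or opposing-gap cell, within simulation error. It was better in those cells when r exceeded 0 and there was either a gap or a drug effect.

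Other points hold in part:

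- The wording of sections 1.1 and 4.2 leans towards group-by-time, so the group-main-effect figures describe a possible misreading, not the likely one. Naming the term removes the doubt.
- The gap is assumed. If it is small and regresses, the harm is slight.
- Control week 0 is undefined. A mistimed control baseline would weaken the covariate. This was not simulated, and the missing-sample costs assume samples are missing at random.
- The calculations treat the groups as independent and ignore the matching.
- The study is exploratory (section 3.4) and already includes longitudinal analyses. That lowers the stakes but does not remove the bias.

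**Conclusion.** The concern holds. For the T-cell and phenotype markers, the primary test discards a baseline planned for enrolled subjects, in a comparison that neither randomisation nor matching balances on that marker. For an assumed 0.5 SD week-0 gap and no drug effect, its false-positive rate is 5–18% if the gap regresses and about 32% if it is stable. An opposing stable gap cuts its power for a 0.8 SD effect from 67% to 14–15%. Baseline adjustment removes the error in the regressing case and reduces it in the stable case, more so as r rises; at r = 0 it gains nothing material. It does not address confounding that acts after week 0.

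These sizes rest on assumed gaps, correlations and normal values; the direction of the improvement does not depend on one chosen value. This is a change the plan should make, with medium confidence because the gap itself is unshown.

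**What to change.** 1. Make the primary between-group analysis of T-cell and phenotype frequencies a rank ANCOVA at week 24, with group and the same marker's week-0 value. Keep the week-24 Mann-Whitney on all controls as a sensitivity analysis.
2. Define each control's week-0 and week-24 samples as the stored samples closest in time since transplant to those of the matched subject, since subjects enter at 0 to 3 months (section 7.2.1). Where the pool allows, require a usable week-0 sample when selecting controls.
3. Keep the repeated-measures ANOVA, name group-by-time as its tested term, and apply a Greenhouse-Geisser correction.
4. Add a between-group Mann-Whitney on change from week 0, on a scale fixed in advance. If it disagrees with the ANCOVA, report the result as not robust to baseline difference. Use this as a reporting label and not as a condition for significance, because requiring both lowers power.

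**Cost.** The covariate takes one degree of freedom (67% v 67% power at r = 0). Comparing controls over time already implies assaying their stored samples. The larger cost is controls without a usable week-0 sample. For r = 0 / 0.3 / 0.5 / 0.7, rank ANCOVA power is 61 / 64 / 71 / 85% with 16 of 20 usable, and 53 / 56 / 63 / 78% with 12. It matches the unadjusted test on all 20 controls (67%) with about 18, 14 and 9 usable controls at r = 0.3, 0.5 and 0.7.

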Test Product, Dose and Mode of Administration, Duration of Treatment: Study patients will receive intravenous belatacept at 5mg/kg every two weeks at day 1 and weeks 2, 4, 6, and 8, and then monthly at months 3, 4, and 5. At month 6 patients may elect to continue for an additional six month period of belatacept administration. Peripheral blood mononuclear cells (PBMCs) and sera for antibody testing will be collected at time of study entry and at 4, 8, 12, and 24 weeks after belatacept start, frozen and banked at our center, and analyzed in batch fashion for development of humoral and cell mediated immunity. Patients who elect to receive an additional 6 months of belatacept treatment will undergo additional immunologic analysis at 1 year after study entry.

Reference Therapy, Dose and Mode of Administration, Duration of Treatment: Immunologic evaluations performed on study patients will be compared with a matched group of 20

control patients receiving conventional immunosuppressive therapy and participating in an ongoing observational trial regarding immunologic mechanisms contributing to rejection in kidney transplant patients.

Criteria for Evaluation:

Primary Outcome Measures:

- Donor specific antibody testing at Month 6
- Cell surface cytokine secretion in response to donor cell antigen by direct and indirect stimulation at Month 6
- Cell surface cytokine secretion in response to CMV and EBV antigens by direct and indirect stimulation at Month 6
- Immunophenotyping to determine overall immune profile at Month 6
- Patient and functional graft survival in stable renal transplant recipients

Secondary Outcome Measures:

- Donor specific antibody testing at Months 1 and 3 (and month 12 if continuing in study)
- Cell surface cytokine secretion in response to donor cell antigen by direct and indirect stimulation at Months 1 and 3 (and month 12 if continuing in study)
- Cell surface cytokine secretion in response to CMV and EBV antigens by direct and indirect stimulation at Months 1 and 3 (and month 12 if continuing in study)

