#### 3.1.2 Overview

This is an open label, single center clinical trial. All subjects will have undergone kidney transplantation with induction immunosuppression and will be on maintenance therapy with a CNI (tacrolimus or cyclosporine) plus mycophenolate mofetil and corticosteroid maintenance therapy at the time of enrollment. 20 subjects with evidence of CNI toxicity (see definition below) in the first three months after transplant will be enrolled to switch to the belatacept regimen. These enrolled subjects will be compared with 20 matched patients from an ongoing observational study of kidney transplant patients at our center.

All subjects will also receive induction with basiliximab and a background maintenance immunosuppressive regimen of MMF and corticosteroids.

Study patients will receive intravenous belatacept at 5mg/kg every two weeks at day 1 and weeks 2, 4, 6, and 8, and then monthly at months 3, 4, and 5. At month 6 patients may elect to continue for an additional six-month period of belatacept administration

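### Controls are chosen by patient-level matching, but the primary month-6 test treats the two groups as independent and no planned between-group analysis uses the matching

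*Combined protocol and SAP*

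**What the plan says.** Section 3.1.2 enrolls "20 subjects with evidence of CNI toxicity" and adds: "These enrolled subjects will be compared with 20 matched patients from an ongoing observational study". Section 3.1.3 gives the criteria: "Matching will be performed based on age within 10 years, sex, deceased versus living transplant, and DSA level at time of enrollment". No tolerance is set for DSA. Section 4.1 states: "Patient matching will be performed in a blinded fashion".

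Other wording is looser. The synopsis, under reference therapy, says: "Immunologic evaluations performed on study patients will be compared with a matched group of 20". Section 4.1 says: "A representative group of 20 control patients receiving standard immunosuppressive medications will be identified". Nowhere is a pair or a 1:1 ratio mentioned.

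For the analysis, the synopsis says: "Comparison between groups will be performed by Mann Whitney U test". Section 4.2 repeats this for DSA, antigen-reactive cell frequencies and immunophenotypes at week 24: "comparison to be performed by Mann Whitney U test". It adds a within-patient comparison of baseline with week 24 and a repeated-measures ANOVA against controls. Neither mentions a pair term or the matching factors, and the data sets described in 4.1 carry no pair identifier. Section 3.4 calls the study exploratory, says power cannot be estimated, and gives no alpha.

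**The concern.** A 10-year age limit has meaning only relative to a particular index patient. Together with equal numbers and matching described patient by patient, it points to one control per switched patient. Month-6 outcomes may then be correlated within pairs. This is most plausible for DSA, because its enrollment value is a matching factor.

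Mann-Whitney takes its null variance from two independent samples. Under positive within-pair correlation that variance is too large, so real differences are harder to detect. The design accepts a restricted choice of controls in order to match, and the analysis then gives up the precision that matching could buy. With 20 patients per group, that precision matters.

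**Working it through.** **Inputs.** From the documents: 20 switched patients and 20 matched controls (3.1.2), matching factors (3.1.3), and the Mann-Whitney test (synopsis, 4.2). Assumed, because not given: two-sided 5%, a true difference of 0.8 SD, and within-pair correlation ρ from 0 to 0.7. The plan has no power figure to reproduce.

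**Direction of the error.** With n pairs and common variance σ², the difference in means has variance 2σ²(1−ρ)/n, while an unpaired test uses 2σ²/n. The true size of a nominal 5% unpaired z test is therefore 2[1−Φ(1.96/√(1−ρ))]:

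- ρ = 0.2: 1.96/√0.8 = 2.19, size 2.8%
- ρ = 0.3: 1.96/√0.7 = 2.34, size 1.9%
- ρ = 0.5: 1.96/√0.5 = 2.77, size 0.6%

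**Simulation of the rank tests** (20,000 trials per setting, 20 complete bivariate-normal pairs; power at 0.8 SD). The exact Wilcoxon signed-rank test serves here only as a benchmark for what pairing is worth.

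| ρ | Mann-Whitney type I error | Mann-Whitney power | Signed-rank power | Difference (points) |
|---|---|---|---|---|
| 0 | 4.8% | 66.5% | 64.7% | −1.8 |
| 0.1 | 3.8% | 67.8% | 69.4% | 1.6 |
| 0.2 | 3.2% | 67.9% | 73.8% | 5.9 |
| 0.3 | 2.2% | 69.6% | 80.0% | 10.4 |
| 0.5 | 0.9% | 72.6% | 91.2% | 18.6 |
| 0.7 | 0.15% | 77.4% | 98.9% | 21.5 |

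Signed-rank type I error stays at 4.9% to 5.1%. With 70% zeros, a DSA-like shape, Mann-Whitney type I error is 4.7%, 3.0%, 1.7% and 0.6% at ρ = 0, 0.3, 0.5 and 0.7. The direction is the same.

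**Which remedy holds up.** Signed-rank drops zero differences and incomplete pairs. Its power against Mann-Whitney at 0.8 SD under less ideal data (the zero and missing rates are assumptions):

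| Setting | ρ | Mann-Whitney | Signed-rank |
|---|---|---|---|
| 70% zeros in controls | 0 / 0.3 / 0.5 | 41 / 36 / 37% | 29 / 28 / 35% |
| 80% zeros in controls | 0 / 0.3 / 0.5 | 28 / 26 / 27% | 12 / 12 / 13% |
| 15% missing per arm | 0 / 0.2 / 0.3 / 0.5 | 59 / 58 / 60 / 61% | 48 / 55 / 63 / 78% |

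With 15% missing independently in each arm, only 20 × 0.85² = 14.5 pairs are complete on average, while each arm keeps 20 × 0.85 = 17 patients.

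A mixed model on rank scores, with group fixed and pair random, uses everyone. In separate runs, so that the Mann-Whitney figures differ slightly from those above, its power at 0.8 SD was:

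| Setting | ρ | Mann-Whitney | Rank mixed model |
|---|---|---|---|
| Complete, continuous | 0.3 | 68% | 78% |
| Complete, continuous | 0.5 | 75% | 91% |
| 15% missing per arm | 0.3 | 60% | 70% |
| 70% zeros | 0.3 | 34% | 41% |

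It lost no power at ρ = 0. Its type I error ran at about 4% to 7%. Where it is above 5%, part of the apparent gain reflects that.

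**The case against.** The strongest reply is that pairing is inferred. The synopsis and 4.1 speak of a group, DSA has no matching tolerance, and under group-level matching there are no pairs to analyze. That stands, and the fix needs a branch for it. It does not rescue the plan, because Mann-Whitney ignores the matching factors in that case too.

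It is also fair to say that a conservative test in an exploratory study does limited harm. A reader might infer from a wrong error rate that the plan risks false positive findings. The calculations show the opposite for any positive correlation. A reader might also infer that every primary immune endpoint is affected. The documents do not support that: T-cell and phenotype measures are not themselves matched on their baseline values, their within-pair correlation may be near zero, and there Mann-Whitney does as well as or slightly better than signed-rank.

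Finally, the textbook answer for matched pairs, signed-rank throughout, can do worse than the planned test. Section 5.2 excludes patients with PRA of 30% or more, so many zero DSA values are plausible, though the documents give no distribution. Controls rely on banked samples from similar time points (4.1), so incomplete pairs are likely. This objection stands against signed-rank as the primary test, but not against a model that keeps all subjects. Nor is a paired test of rejection called for, since section 4.2 only summarises rejection rates.

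**Conclusion.** The point holds in a limited form. The plan matches controls on patient-level criteria and then names an independent-samples test, with no between-group analysis that uses the matching. If pairs exist and outcomes correlate positively within them, the test is conservative and loses power, by the amounts given in the table. At correlation near zero there is little or no loss.

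This rests on one-to-one matching, which is the best reading but not stated, and on assumed values for alpha, effect size and correlation. No figure in the plan is falsified, because it states no alpha or power. The change is still worth making: it is cheap, and the sample is too small to waste information.

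**What to change.** 1. State in 3.1.3 and 4.1 whether matching is one-to-one, and carry a pair identifier in the 4.1 data sets.
2. If it is one-to-one, make the primary between-group comparison in the synopsis and 4.2 a mixed model on rank scores (or suitably transformed values), with group as fixed effect and matched pair as random effect. Include all subjects, also those in incomplete pairs. Name the small-sample degrees-of-freedom method.
3. Add the pair term to the repeated-measures model.
4. Keep Mann-Whitney as a sensitivity analysis. Do not make signed-rank the primary test for all endpoints.
5. If matching is only at group level, adjust the rank model for age, sex, donor type and enrollment DSA instead of fitting pairs.

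The cost is a few sentences, one variable and somewhat more modelling work, plus a small-sample approximation whose type I error was about 4% to 7% in simulation. The choice should be fixed before the batched assay results are analyzed.
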